Patients who have been enrolled in the study but are no longer eligible to receive study treatment for reasons other than progression are allowed to receive vaccines that have been generated for them at the discretion of the PI. They will be replaced for purposes of study endpoint if they do not meet criteria of an evaluable subject (received standard XRT/TMZ and received at least one DC vaccine). Such subjects would include: subjects who do not complete standard radiation treatment with concomitant TMZ, have prolonged interruption of treatment beyond allowable study guidelines. These patients will be included in the intent to treat analysis but excluded from the evaluable subjects analysis if disqualified prior to receiving first vaccine. Such subjects may receive QA/QC qualified DC vaccines according to study schedule with or without TMZ at discretion of the PI and in consultation with the treating neuro-oncologist (i.e. subjects removed for intolerance of TMZ treatment may discontinue or reduce TMZ dose as clinical management would dictate).

Given absence of curative treatment for GBM, release of vaccines to patients who have consented to the study but are unable to meet study requirements (most often chemotherapy intolerance) is deemed in best interest of the enrolled subjects and best utilization of cGMP manufactured autologous products. While these patients may be excluded from primary endpoint analysis of evaluable subjects, all toxicity monitoring and DLT stopping rules will apply to any subjects receiving DC vaccination.

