15 STATISTICAL METHODS AND DATA ANALYSIS

15.1 Study Design Overview

The primary goal of this randomized phase II study is to determine whether the addition of pp65-LAMP mRNA DC vaccination in adult patients with newly-diagnosed GBM receiving dose-intensified TMZ will be a treatment worthy of investigation in a large phase III study. A secondary

objective will be examination of the immunologic responses induced by full-length vs short LAMP sequences.

Although this randomized phase II study is comparative, it will not be definitive as the assessment will be conducted with a large false-positive rate. We have included a concurrently followed control arm in the trial design in lieu of a historical control group to ensure that appropriate comparisons can be made without concern that the patients receiving standard treatment differ in prognostic factors or standards of care (Rubinstein, 2009; Ratain and Sargent, 2009; Rubinstein et al., 2005).

We will randomize eligible patients, after enrollment, to one of 3 study arms in which they will receive 21-day TMZ concurrently with one of the following treatments:

Arm #	Vaccine	Skin Preparation
1	pp65-shLAMP mRNA DCs with GM-CSF	Tetanus
2	pp65-fLAMP mRNA DCs with GM-CSF	Tetanus
3	PBMCs	Saline

Randomization will be stratified by:

- Age 69 years old and younger; or 70 years old and older
- RPA Class (III, IV, or V)
- CMV seronegative or seropositive

We will use a permuted block randomization scheme with a 1:1:1 study arm allocation ratio and a block size of 6 within each stratum.

Adapted RPA Stages For Malignant Gliomas (Survival With Concurrent Temozolomide and Radiation Therapy vs Radiation Therapy alone)				
Stage	Characteristics	Median OS	2-year OS	p-value vs. control
III	Age <50, PS 0	21 vs. 15 mo	43% vs. 20%	p<0.0001
IV	Age <50, PS 1-2 Age >=50, Surgery, MMSE >=27	16 vs. 13 mo	28% vs. 11%	p<0.01
V	Age >=50 and either Biopsy only or MMSE <27	10 vs. 9 mo	17% vs. 6%	p=0.05

Approximately 200 patients will be enrolled in the study, randomized and receive “standard-of-care” radiotherapy concurrent with TMZ under the assumption that approximately 120 patients will be vaccinated according to treatment arm.

A Data Sharing Agreement has been established with Immunomic Therapeutics, Inc. and the University of Florida. A Limited Data Set will be sent to evaluate immunogenicity and clinical efficacy of the vaccine products used within this clinical trial (for patients treated at the UF site

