We therefore used 13.8 months as the median OS reference level for our control group and assumed Weibull-distributed OS times with a common shape parameter value for both the treatment and control groups. This is equivalent to assuming Weibull-distributed OS times with proportional hazards between the treatment and control groups.

Using methods adapted from Wu and Xiong (2014), we calculated improvement in median OS (or equivalently, the largest treatment vs. control hazard ratio less than 1) that could be detected by a log rank test with 90% power at 1-sided $\alpha=0.20$, for selected Weibull shape parameter values ranging from 1.00 (equivalent to exponential survival with constant hazard) to 1.25 (accelerating hazard). We assumed 120 patients would be randomized and proceed to vaccination at a uniform rate over a 3-year accrual period. These patients would then be followed after the end of accrual for one additional year. As summarized in the following table, 77 deaths (expected by follow-up

times ranging from 45.1 to 48.9 months, depending on the degree of hazard acceleration assumed) will allow a treatment vs. control hazard ratio of 0.6 to be detected with sufficient power. Equivalently, improvement in median OS ranging from 7.0 to 9.2 months (again, depending on the degree of hazard acceleration assumed) can be detected with sufficient power.

Improvement in median overall survival (Surv50) that can be detected at 90% power and a one-sided alpha-level of 0.20, for possible Weibull shape parameters characterizing the degree of hazard acceleration:

Weibull			Detectable effect at 90% power, 1-tail alpha=0.20		
TRT:	Shape	Baseline hazard function trend	Expected # of months to observe 77 deaths	Surv50 (months)	Hazard ratio
CTL N	parameter				
80:40	1.00	Constant (exponential survival)	48.9	+ 9.2	0.60
80:40	1.16	Accelerating (Gilbert et al)	46.3	+ 7.6	0.60
80:40	1.20	Accelerating (Stupp et al)	45.7	+ 7.3	0.60
80:40	1.25	Accelerating	45.1	+ 7.0	0.60

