15.3 Analytic Methods

15.3.1 Primary Objective and Secondary Clinical Objectives

We will use Kaplan-Meier survival curves and the log rank test to characterize and compare PFS and OS in patients who received pp65-LAMP mRNA DC vaccine (Arms 1 and 2) and in control patients (Arm 3). PFS is defined as the time between first vaccination and first documentation of either disease progression/recurrence, or death without prior progression/recurrence. Patients remaining alive without disease progression will have PFS censored at last follow-up. OS will be defined as the time between first vaccination and death, and will be censored at the last follow-up if death has not occurred. We will also perform a stratified analysis incorporating the three stratification variables (age, RPA class, and CMV sero-status) using Cox proportional hazards regression. The index day for all of our primary comparisons will be the time of the first vaccination. Because patients who fail to proceed to the first vaccination because of GBM recurrence or for other reasons cannot experience differential effects due to treatment arm membership, we will not perform an intent-to-treat analysis that includes these patients. We will perform an intent-to-treat analysis of OS and PFS that includes patients who begin the vaccination sequence but who do not receive at least three vaccinations because of recurrence or other reasons. OS and PFS times for adequately vaccinated patients who are lost to follow-up will be considered right-censored at the time of loss and will be included in all of our survival comparisons.

All subjects who receive at least one dose of DC vaccine will be considered evaluable for purposes of safety and toxicity.

All subjects who complete chemoRT and receive dose-intense adjuvant TMZ and at least 3 DC vaccines will be considered evaluable for purposes of the primary and secondary endpoints.

The impact of pp65-LAMP mRNA DC vaccine on PFS and OS in patients with gross total resection will also be explored using the log rank test and Kaplan-Meier curves, although our trial design may not necessarily achieve sufficient power to detect a clinically meaningful effect within this patient subgroup.

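### Sections 15.3.1 and 9.8 define the evaluable set for the primary endpoint differently (three vaccines plus dose-intense adjuvant TMZ, versus one vaccine), and the stated power belongs to the one-vaccine set

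*Combined protocol and SAP*

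**What the plan says.** Four places bear on who is in the primary OS comparison.

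- **15.3.1, evaluability.** Patients that "complete chemoRT and receive dose-intense adjuvant TMZ and at least 3 DC vaccines will be considered evaluable for purposes of the primary and secondary endpoints". In the same section, OS and PFS start at the first vaccination.
- **9.8, evaluability and replacement.** An evaluable subject is one who "received standard XRT/TMZ and received at least one DC vaccine". Of patients who lose eligibility for reasons other than progression, it says: "They will be replaced for purposes of study endpoint if they do not meet criteria of an evaluable subject". It then ties this to the main test: "While these patients may be excluded from primary endpoint analysis of evaluable subjects".
- **15.2 and 15.1, sample size.** "We assumed 120 patients would be randomized and proceed to vaccination at a uniform rate over a 3-year accrual period", and enrollment of about 200 is planned "under the assumption that approximately 120 patients will be vaccinated according to treatment arm".
- **15.3.1 and 9.8, intent-to-treat.** For patients who never reach vaccine 1, 15.3.1 says "we will not perform an intent-to-treat analysis that includes these patients". It does plan an intent-to-treat analysis that takes in patients who start vaccination but receive fewer than three doses. Section 9.8 says that ineligible patients will be "included in the intent to treat analysis but excluded from the evaluable subjects analysis if disqualified prior to receiving first vaccine".

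Under 9.1 and 9.5, patients aged 70 or older, and those with grade 3 or higher hematologic toxicity from TMZ during chemoradiation, receive standard-dose rather than dose-intensified adjuvant TMZ. Age (69 or younger, 70 or older) is a randomization stratum in 15.1 and one of the stratification variables in the planned Cox analysis in 15.3.1.

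**The concern.** Both definitions claim the primary endpoint. A patient with one or two vaccines counts as evaluable under 9.8, so is not replaced, but is not evaluable under 15.3.1. The wording leans toward an evaluable set as primary without saying which one. The OS comparison could therefore be run on sets of different size and selection, and the choice could be made after survival is known.

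If the 15.3.1 definition is applied as written, two things follow.

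- **Selection after the index day.** OS starts at vaccine 1, but entry requires vaccine 3. Whatever stops a patient in between removes that patient, including the recurrence that 15.3.1 itself names as a reason for falling short of three.
- **A population conflict.** Read literally, the dose-intense condition removes patients whom the protocol assigns to standard-dose TMZ. For the two groups above this is settled before vaccine 1, so it is not selection on later events. It does contradict stratifying the randomization and the Cox analysis by age.

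**Working it through.** **Step 1. Which set carries the stated power?** Inputs from 15.2: one-sided alpha 0.20, power 0.90, hazard ratio 0.60, 80:40 allocation, control median 13.8 months, 36-month uniform accrual, 120 vaccinated patients.

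Schoenfeld deaths: (0.8416 + 1.2816)² / [(2/3)(1/3)(ln 0.60)²] = 4.508 / 0.0580 = 77.7, against 77 in the plan.

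Power at 77 deaths: Φ(√(77 × 2/9) × 0.5108 − 0.8416) = Φ(1.27) = 0.898.

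With survival S(t) = exp[−HR × ln 2 × (t/13.8)^shape], 77 of 120 deaths fall at 48.7, 46.2, 45.7 and 45.1 months for shapes 1.00, 1.16, 1.20 and 1.25. The plan gives 48.9, 46.3, 45.7 and 45.1. The median gains, 13.8 × [(1/0.6)^(1/shape) − 1], are 9.2, 7.6, 7.3 and 7.0 months, as in the plan. The 90% therefore belongs to all 120 vaccinated patients.

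**Step 2. The gap between vaccine 1 and vaccine 3.** Section 9.8 gives two intervals of 2 (±1) weeks: 2 × 1 = 2 to 2 × 3 = 6 weeks, nominally 4. Under the plan's Weibull model, control deaths by 4 weeks are 2.7% (shape 1.20) to 4.5% (shape 1.00). Most exclusions would therefore have to come from progression, toxicity or the TMZ condition, and the documents give no rates for these.

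**Step 3. Power if the 15.3.1 set is used.** The excluded share is assumed, equal in both arms, with HR still 0.60 and shape 1.20.

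| Excluded | Patients | Deaths at 45.7 months | Power | Months to 77 deaths |
|---|---|---|---|---|
| 0% | 120 | 77 | 0.90 | 45.7 |
| 10% | 108 | 69.4 | 0.88 | 50.5 |
| 20% | 96 | 61.7 | 0.85 | 58.3 |
| 30% | 84 | 54.0 | 0.82 | 75.7 |

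With an assumed accrual of 60 to 72 months and a data cut at 90 months, power is 0.93–0.94, 0.91–0.92 and 0.89–0.90 for the three reduced sets.

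**Step 4. False-go rate if the vaccine has no effect.** Simulation: 80:40, shape 1.20, cut at the 77th death of the full 120, one-sided log rank test at 0.20, 10,000 runs per cell (Monte Carlo error about √(0.2 × 0.8/10,000) = 0.004). Excluded patients are drawn at random from the shortest-surviving quarter or half of each arm, or regardless of survival. With no exclusions the rate is 0.207.

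| Excluded, DC / control | Shortest quarter | Shortest half |
|---|---|---|
| 5% / 2.5% (4 and 1 patients) | 0.257 | 0.231 |
| 7.5% / 5% | 0.255 | 0.241 |
| 10% / 5% | 0.307 | 0.269 |
| 2.5% / 5% | 0.177 | 0.174 |
| 5% / 10% | 0.135 | 0.149 |
| 5% / 5% | 0.207 | 0.205 |
| 10% / 10% | 0.214 | 0.202 |

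Exclusions unrelated to survival give 0.201 to 0.213. Repeat runs agree with the table to within about 0.01. Longer follow-up does not remove the shift: with 66-month accrual and a cut at 90 months, the quarter scenario gives 0.251 (5/2.5), 0.298 (10/5) and 0.145 (5/10), against 0.211 with no exclusions.

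**The case against.** **The order of analyses can be inferred.** 15.3.1 states who is evaluable for the primary endpoint, 9.8 speaks of a primary analysis of evaluable subjects, and the amendment log calls the intent-to-treat analysis a subanalysis. This stands as far as it goes: an evaluable set probably leads. It does not settle whether one vaccine or three makes a patient evaluable.

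**The numerical harm is modest and conditional.** This largely stands. The power loss is small and mostly disappears with the longer accrual that the amendment log reports (more than four years). If the vaccine affects neither survival nor progression, losses from death and progression should balance across arms, and balanced cells stay near 0.20. Bimonthly imaging, confirmation of progression at least 4 weeks later, allowed continuation and make-up vaccines all limit removals in so short a window. One arm-related route is in the text: section 13.1 withdraws patients with grade II or higher urticaria, and only the DC arms receive GM-CSF and Td skin preparation. It need not track survival. Section 15.1 also says openly that the trial is not definitive.

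**Literal readings can be pushed too far.** Some inferences are tempting but not supported:

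- *That 9.8 and 15.3.1 require opposing TMZ regimens.* In 9.8 the standard XRT/TMZ condition is concurrent chemoradiation, which 15.3.1 also requires. The differences are three vaccines against one, and the added adjuvant dose-intense condition.
- *That patients aged 70 or older are definitely meant to be left out.* The age-stratified Cox analysis points the other way. Taken equally literally, the DC vaccine wording would exclude the whole PBMC control arm. The wording needs repair, but an intended exclusion is not established.
- *That the two intent-to-treat statements flatly contradict each other.* Section 9.8 lets disqualified patients receive their vaccines, and those who do have a first vaccination. The conflict covers only disqualified patients who never receive one.

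**Conclusion.** The inconsistency is real and sits in the current text: three vaccines plus dose-intense adjuvant TMZ in 15.3.1, one vaccine in 9.8, and a sample size built on the one-vaccine set. The plan does not say which definition governs the deciding test. If the 15.3.1 definition is used, the set is selected on events after the index day and, read literally, drops patients treated as the protocol directs.

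The size is illustrative, because every exclusion share above is assumed. Power would be about 0.88, 0.85 or 0.82 at 10, 20 or 30% exclusion and the planned 45.7 months, largely recovered with longer accrual and follow-up. The false-go rate stays near 0.20 if exclusions are balanced or unrelated to survival. Only if they are unequal by arm and concentrated in the shortest survivors does it move to about 0.25–0.31 or 0.14–0.18. The direction is unknown.

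A reader might infer that the trial is underpowered or that its false-positive rate is inflated; the documents establish neither. This is a should-fix point: the primary set must be settled before OS is compared by arm, but serious distortion is not shown.

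**What to change.** In 15.3.1, name one primary set that matches 15.2: *all randomized patients who received at least one study vaccine (DC or PBMC), analyzed as randomized, with OS from first vaccination, whatever the number of vaccines or the TMZ regimen received.* State that the log rank test of OS in this set, at one-sided 0.20, is the deciding analysis. Then:

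- State one rule for patients disqualified before vaccine 1 but vaccinated later. Either include them in this set, or exclude them as 9.8 does and bring them in through a sensitivity analysis. Word the set definition to match.
- Patients never vaccinated have no index day. Leave them out of these analyses, or include them only in an analysis timed from randomization. Align the intent-to-treat wording of 9.8 with 15.3.1.
- Make the at-least-three-vaccine set supportive, with time counted from vaccine 3, in line with the landmark analysis in 15.3.2.
- Write study vaccine for DC vaccine in the endpoint evaluability definitions.
- Reconcile the dose-intense wording of 15.3.1 and of the primary objective (5.2.1) with the TMZ passages in 9.1 and 9.5. Which regimen is right is not a matter for this review.
- Record the change in a dated amendment made without sight of OS by arm. If that cannot be shown, report OS in both sets side by side and say so.

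The cost is a late amendment to a single-blind trial, where it may be hard to document that those choosing the set had not seen OS by arm. The primary set will also mix two TMZ regimens, though age, which determines part of that split, is already a stratum. No new patients or data are needed.

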9 INVESTIGATIONAL PLAN

9.1 Overview

The eligibility criteria for this trial will be similar to those used in the RTOG 0525 study (Aldape 2009). Prior to the initiation of TMZ and external beam RT, patients will sign consent and undergo leukapheresis for PBMCs in accordance with **SOP-UFBTIP-131**.

Up to 200 newly diagnosed WHO Grade IV glioma patients will be enrolled in the study. Eligible patients will be randomized, undergo leukapheresis and receive “standard-of-care” radiotherapy concurrent with TMZ under the assumption that approximately 120 patients will be vaccinated according to treatment arm in this placebo controlled, single blinded, randomized Phase II study.

Prior to leukapheresis, patients will be randomized to receive one of three treatment regimens with dose-intensified TMZ treatment at 100 mg/m²/day for 21 days with an allocation ratio of 1:1:1 into one of three arms to receive:

- 1) pp65-shLAMP mRNA DCs with GM-CSF 150 µg (Td skin prep)
- 2) pp65-fLAMP mRNA DCs with GM-CSF 150 µg (Td skin prep)
- 3) Unpulsed PBMCs (saline skin prep)

Randomization will be stratified by;

- Age 69 years old and younger, who will receive dose-intensified adjuvant temozolomide; or 70 years old and older who will receive standard dose adjuvant temozolomide.
- Recursive Partitioning Analysis (RPA) class (III, IV, or V). To determine RPA class, Performance Status (PS) will be determined from KPS conversion using the ECOG comparison scale for patients ≤ 50 years; a Mini-Mental State Examination will be performed at enrollment for patients ≥ 50 years.
- CMV seronegative or seropositive

Within 7 weeks of surgery, patients will undergo standard RT with concurrent TMZ at a target dose of 75 mg/m²/day.

Patients will receive the initial cycle of TMZ 4 (+/- 1) weeks after completing RT. Study drugs will be given intradermally at day 22-24 after the first TMZ cycle and divided equally between both inguinal regions in accordance with **SOP-UFBTIP-128**. All patients will receive Td booster (5 Lf) with vaccine #1 regardless of booster history. Vaccine #2 and #3 will occur at 2 week intervals.

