Appendix B, C and D are provided as guidelines for dose modifications and chemo management.

Patients age 70 and above, will receive standard dose Temozolomide at 150-200 mg/m²/day for 5 consecutive days of a 35 (+/7) days cycle. For these subjects, one dose reduction to 100 mg/m²/day for 5 days will be allowed based on AE on previous cycle.

In the event that chemo adjuvant cycle is delayed past the timeframe provided in Appendix C and D, the treatment with Temozolomide may resume when toxicity has resolved (or returned within treatment limits) if patient has not experienced tumor progression at the discretion of the PI in consultation with the treating physician, if the PI believes that it is safe to continue therapy and that the patient may benefit from additional chemo cycles. Study vaccines will be given at day 22-24 of each cycle when chemo is restarted.

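### Section 15.3.1's evaluable set for the primary endpoint (dose-intense TMZ and at least three vaccines) contradicts the at-least-one-vaccine population of 9.8 and 15.2, and the plan does not say which analysis decides

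*Combined protocol and SAP*

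**What the plan says.** Section 15.3.1 compares OS and PFS between Arms 1 and 2 combined and Arm 3 by log rank test, with a stratified Cox analysis on age, RPA class and CMV serostatus. For time zero it states: "The index day for all of our primary comparisons will be the time of the first vaccination". It then restricts evaluability. Patients must complete chemoradiation and "receive dose-intense adjuvant TMZ and at least 3 DC vaccines will be considered evaluable for purposes of the primary and secondary endpoints". The same section plans an analysis that it calls intent-to-treat, which "includes patients who begin the vaccination sequence but who do not receive at least three vaccinations".

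Other current sections describe a different population:

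- **9.8** speaks of an "evaluable subject (received standard XRT/TMZ and received at least one DC vaccine", and says that patients who lose eligibility are "excluded from the evaluable subjects analysis if disqualified prior to receiving first vaccine".
- **15.2** assumes that 120 patients are randomised and proceed to vaccination, and derives the 77 deaths from them. **15.1** plans enrolment so that about 120 are vaccinated.
- **9.1** stratifies randomisation at age 69/70 and treats the two TMZ regimens as distinct: the younger group are those "who will receive dose-intensified adjuvant temozolomide; or 70 years old and older who will receive standard dose adjuvant temozolomide".
- **9.5** repeats the age rule ("Patients age 70 and above, will receive standard dose Temozolomide") and also assigns the 5-day schedule after TMZ-related hematologic toxicity of grade 3 or higher during chemoradiation.

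**The concern.** A patient who received two vaccines, or who received the 5-day TMZ schedule that the protocol prescribed, counts under 9.8 and 15.2 but not under the evaluability rule of 15.3.1. Three consequences follow if that rule is applied as written.

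1. The TMZ clause drops patients who were enrolled, stratified and treated as directed. It empties the 70-and-older stratum, so the age factor in 15.3.1's stratified Cox model has only one level left.
2. The three-vaccine clause conditions on reaching vaccine 3, although follow-up time starts at vaccine 1. Deaths and progressions between the two are removed after the time origin.
3. The set tested is not the set that 15.2 powers.

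The phase III recommendation rests on one OS comparison at a one-sided alpha of 0.20. With two defensible populations in the text, the choice between them should not remain open when survival by arm is known.

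**Working it through.** **Reproducing the plan's figures.** Inputs from 15.2: HR 0.60, one-sided alpha 0.20, 90% power, 80:40 allocation, control median 13.8 months, uniform accrual over 36 months, then 12 months of follow-up.

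- Schoenfeld events: (0.8416 + 1.2816)² / [(2/3)(1/3)(ln 0.60)²] = 4.508 / 0.0580 = 77.7, rounded up to 78. The plan states 77.
- Power with 77 deaths: Φ(√(77 × 2/9) × 0.5108 − 0.8416) = Φ(1.27) = 0.898.
- With Weibull shape 1.20, the 77th death is expected at 45.7 months, as in the plan's table.

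These figures belong to the population of all vaccinated patients. Neither the TMZ clause nor the three-vaccine clause enters them.

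**A limit that needs no assumption.** The strict set can reach 77 deaths only if at least 77 of the 120 patients qualify (77/120 = 64%). If more than 120 − 77 = 43 are excluded, it never can.

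**TMZ clause.** The documents do not give the share of patients on 5-day TMZ, so a share s is assumed, equal across arms and with the same survival. Expected deaths are (1 − s) times those in the vaccinated set. Shape is 1.20 and HR 0.60, and the power formula is the one above.

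| Assumed s | Deaths at 48 months | Power at 48 months | Month of 77th death |
|---|---|---|---|
| 0 | 81.4 | 0.908 | 45.7 |
| 10% | 73.2 | 0.889 | 50.5 |
| 20% | 65.1 | 0.865 | 58.3 |
| 30% | 57.0 | 0.835 | 75.7 |

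**Three-vaccine clause, deaths only.** Sections 9.8 and 10.7 (footnote 13) space vaccines 2 and 3 at 2 (±1) weeks, so vaccine 3 falls 2 to 6 weeks after vaccine 1, nominally 4. P(death by t) = 1 − exp[−ln 2 × HR × (t/13.8)^1.20].

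- 4 weeks: 2.65% of controls and 1.60% of treated patients, or 40 × 0.0265 + 80 × 0.0160 = 1.1 + 1.3, about 2 deaths.
- 6 weeks: 4.28% and 2.59%, or 1.7 + 2.1, about 4 deaths.

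Early progression would remove more patients, but the documents give no rate for it.

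**How often the two sets would disagree.** Trials were simulated under the same model (8,000 per case). Vaccine 3 was at 4 weeks, and the data cut was at the 77th death in the vaccinated set, a cut-off that the plan does not fix. With the three-vaccine clause alone (s = 0), the strict set keeps power of about 0.90, and the two sets give opposite go/no-go answers in about 2% of trials at HR 0.60 and 4-5% at HR 1. With both clauses and s from 10 to 30%, disagreement is about 6-13% at HR 0.60 and 9-14% at HR 1. Most of that comes from the assumed share.

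**The case against.** The strongest reply is that 15.3.1 does name its set. It states a rule for the primary and secondary endpoints and adds an analysis for patients with fewer than three vaccinations, so both vaccine counts are already planned. That is fair. The defect is a contradiction between sections, not silence, and on the vaccine count the fix mainly settles which analysis leads. The added analysis does not mention TMZ regimen, however, and the plan does not say which result decides.

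A second reply is that the TMZ wording is shorthand. Section 15.1 says that all arms receive 21-day TMZ, 9.1 introduces dose-intensified TMZ for everyone before giving the age exception, and the age-stratified Cox analysis makes sense only if older patients stay in. This is plausible, and if it is right no stratum is lost. But 9.1 and 9.5 treat the regimens as different, and the hypothesis and primary objective (5.1, 5.2.1) refer to dose-intensified TMZ, which supports the strict reading. The text has to choose.

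A reader might also infer that no control patient is evaluable, because Arm 3 receives PBMCs and the rule says DC vaccines. The documents do not support that as the intended meaning. Section 15.3.1 names Arm 3 as the comparator, and the protocol uses the term loosely elsewhere: 9.1 has all patients undergo repeat leukapheresis to generate DC vaccines, and 9.8 has the same slip. The wording should be corrected, but controls are not lost in substance.

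Finally, the power loss is modest, depends on an assumed share, and can be recovered because patients are followed until death. All of that stands.

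**Conclusion.** The concern holds as a conflict between current sections. The evaluability rule in 15.3.1 cannot be reconciled with 9.8 on vaccine count, with 15.2 on the powered population, or with 9.5 and the age stratification on TMZ regimen. The three-vaccine clause also selects on events after time zero.

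Its numerical size cannot be fixed from the documents. For an assumed 10-30% on 5-day TMZ, power at 48 months is 89-84% instead of about 91%. The month figures further assume the 36-month accrual of 15.2. The three-vaccine clause alone, counting deaths only, changes little.

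Two stronger conclusions should not be drawn. The first is that the TMZ clause biases the comparison between arms: the regimen rule is the same in every arm, and both triggers (age, and toxicity during chemoradiation) precede vaccine 1. The second is that the trial is seriously underpowered: simulated type I error in the strict set stays near 0.20, and longer follow-up restores the deaths unless more than 43 of the 120 are excluded. What matters is that the deciding analysis is settled in the text. This should be corrected.

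**What to change.** In 15.3.1, define the primary OS and PFS set as all randomised patients who received at least one study vaccine (DC or PBMC), whatever adjuvant TMZ regimen 9.5 assigned, analysed by randomised arm. State 9.8's exclusion of patients disqualified before vaccine 1 in the same words in both sections. Say that the go/no-go decision comes from this set. Keep the set with dose-intense TMZ and at least three study vaccines as a named sensitivity analysis. Replace DC vaccine with study vaccine in the evaluability wording of 9.8 and 15.3.1. The change log (versions 20200323 and 20210810) supports this choice, since it describes the 120-patient target as patients with at least one study vaccine.

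The cost is text only: no new patients, procedures or dosing changes. Timing matters, because the trial is single-blind and the latest logged version is dated 20241007. Make the change before OS is analysed by arm. If it has already been analysed, which the documents do not show, report both sets and disclose when the choice was made. One small downside remains: the primary set mixes two TMZ regimens while 5.2.1 speaks of dose-intensified TMZ, and the report should say so.
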